#### **7.2.4 Interim analyses and data monitoring**

Interim analyses are not planned.

#### **7.2.5 Multicentre studies**

This is a single centre study.

#### **7.2.6 Multiplicity**

For the primary comparisons, there is only one primary comparison in each group, thus multiplicity correction is not needed. For secondary comparisons, where several treatments are included, all pairwise comparisons will be adjusted according to Tukey method.

#### **7.2.7 Examination of subgroups**

No subgroup analyses are planned.

#### **7.2.8 Checking model assumptions**

Assumptions for parametric testing will be checked by visual inspection of residuals. If the residuals do not follow normal distribution closely enough, non-parametric comparison methods (e.g. Kruskal-Wallis test for PK variables) or use of transformation will be considered.

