1.2.1 Rationale of the study design

A crossover design was chosen for this study in order to reduce the impact of inter-individual variability on levodopa PK parameters. This design has been previously used successfully in similar PK studies. Open-label study drug administration is regarded appropriate, because the primary study variables are PK parameters derived from drug concentrations in plasma. Administration of carbidopa and COMT inhibitor for 6 days before levodopa administration will ensure clinically adequate AADC and COMT inhibition when assessing levodopa PK on day 7. There will be a wash-out period of at least 4 days between the study treatment administrations. The length of the wash-out period is considered sufficient for the elimination of levodopa, carbidopa and ODM-104.

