## 3 Overall study design and plan

This is a phase I, open, repeated dose, randomised PK study in healthy males. The study will be conducted at one centre.

The study will consist of 4 parallel groups (Groups 1-4). All groups will have a crossover design with 4 treatment periods, each lasting for 7 days. The total duration of the study will be approximately 10-15 weeks for each study subject.

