## 5 Statistical hypotheses

The primary variable for the evaluation of PK of levodopa is  $AUC_{0-24}$  to describe the total levodopa exposure. Primary comparison will be made within levodopa dose level groups, between crossover treatment arms levodopa / 12.5, 25 or 37.5 mg of carbidopa and levodopa / 65 mg of carbidopa / 100 mg of ODM-104. I.e. comparisons A1 vs. D1, A2 vs. D2, A3 vs. D3, and A4 vs. D4 will be the primary ones.

Other crossover comparisons will be performed and considered as secondary. Parallel group comparisons may be performed. The conclusions on possible differences between treatments will be based on both overall evaluation of levodopa concentration-time profiles and formal statistical analyses of PK parameters.

$H_0: AUC_{0-24, \text{levodopa/carbidopa / ODM-104}} = AUC_{0-24, \text{levodopa/carbidopa}}$

$H_1: AUC_{0-24, \text{levodopa/carbidopa / ODM-104}} \neq AUC_{0-24, \text{levodopa/carbidopa}}$

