## 6 Determination of sample size

The sample size estimation is based on earlier ODM-104 phase I study 3112003. Sample size is estimated using the  $AUC_{0-24}$ . Sample size estimation is based on the results from 12 subjects that completed treatment periods with levodopa 100 mg / carbidopa 25 mg / entacapone 200 mg and MR levodopa 100 mg / carbidopa 65 mg / ODM-104 100 mg. The latter treatment arm with ODM-104 and 65 mg of carbidopa increased exposure by 22% ( $AUC_{0-24}$  14022.2 vs. 17092.6). Within subject variability is estimated to be 0.1386 ( $\sqrt{MSE}$  in logarithmic scale). It is assumed that MR levodopa 100 mg / carbidopa 65 mg / ODM-104 100 mg will increase exposure by 40% compared to MR levodopa 100 mg / carbidopa 25 mg.

When the sample size in each sequence is 3 (with a total sample size of 12), a crossover design will have 80% power to detect a difference in means of 0.336 assuming that the within subject variation is 0.139 using a crossover ANOVA with a 0.1 two-sided significance level. To allow drop outs 14 subjects per group and 56 subjects in total will be randomized into this study with 4-treatment, 4-period William's crossover design. This will provide adequate power for the primary comparison. In case there are premature discontinuations the sponsor will decide case-by-case whether replacement subjects will be entered into the study. Replacement subjects will be randomized to go through all 4 treatment periods. Discontinued study subjects are not allowed to re-enter the study.

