#### **7.2.11 Methods for handling multiple time points**

PK parameters Cmax, AUC, tmax and t1/2 will be calculated and used in statistical comparisons. When modelling PK parameters that are calculated by dosing intervals, treatment by dosing interval interaction will be included in the statistical models.

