#### 8.4.1 Primary PK parameter

The primary PK variable for the evaluation of PK of levodopa is AUC0-24 to describe the total levodopa exposure. The primary PK variable will be summarised using descriptive statistics by treatment and analysed using a mixed linear model with 90% CI applicable for the crossover design. The statistical model will include treatment and period as fixed effects and subject as a random effect. Sensitivity analysis adjusted for subject weight and age will be performed.

The following SAS-code for the primary comparison will be applied:

```
proc mixed data=pkparam2 plots=all alpha=0.10;
  class subject trtpcd visit;
  model log_auc = trtpcd visit / ddfm=KR outp=Resid solution;
  random subject;
  lsmeans trtpcd / diff cl alpha=0.10;
  ods output tests3=testCross lsmeans=lsmeansCross
  diffs=diffscross;
  by group;
run;
```

The following SAS-code for the sensitivity analysis will be applied:

```
proc mixed data=pkparam2 plots=all alpha=0.10;
  class subject trtpcd visit;
  model log_auc = trtpcd visit weightkg age / ddfm=KR outp=Resid
solution;
random subject;
lsmeans trtpcd / diff cl alpha=0.10 adjust=tukey ADJDFE=ROW;
ods output tests3=testCross2 lsmeans=lsmeansCross2
diffs=diffscross2;
by group;
run;
```

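### The only non-parametric fallback named in SAP 7.2.8 is Kruskal-Wallis, an independent-groups test that ignores the pairing in this crossover and is severely conservative

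*SAP*

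**What the plan says.** SAP 7.2.8 has residuals inspected visually. "If the residuals do not follow normal distribution closely enough", then "non-parametric comparison methods (e.g. Kruskal-Wallis test for PK variables) or use of transformation will be considered". Kruskal-Wallis is the only non-parametric test named in either document. No paired or crossover rank method appears.

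The design and the main analysis are within subject:

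- SAP 3: "All groups will have a crossover design with 4 treatment periods".
- Protocol 1.2.1: "A crossover design was chosen for this study in order to reduce the impact of inter-individual variability on levodopa PK parameters".
- SAP 5: "comparisons A1 vs. D1, A2 vs. D2, A3 vs. D3, and A4 vs. D4 will be the primary ones". Each of these is a contrast between two treatments given to the same men.
- SAP 8.4.1: "The statistical model will include treatment and period as fixed effects and subject as a random effect".

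SAP 7.2.9 already makes the log scale the default for at least AUC and Cmax. SAP 7.2.1 promises 90% confidence intervals as well as p-values between treatments.

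On tmax and t½ the SAP is not consistent. SAP 7.2.11 lists them among parameters that "will be calculated and used in statistical comparisons". SAP Table 2 gives them no statistical-analysis footnote, and the output list in SAP 10.1 has only single tables for them, with no matching statistical-analysis table.

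**The concern.** Kruskal-Wallis ranks all observations together as if each treatment had been given to different people. In a crossover, the differences between subjects then stay in the ranks as noise, which is the variability the design was chosen to remove. The test's reference distribution also assumes independence, which fails here because a subject's four values are positively correlated. With positive correlation the test is conservative, so p-values come out too large. The period effect in the planned model is dropped as well, and the test yields no treatment ratio or interval.

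The study is meant to support the choice of carbidopa and ODM-104 doses (Protocol 1.2). If the fallback were used, the risk is that a real difference, particularly a moderate one such as a single dose step, is reported as no difference. The method is best fixed in advance, because the trigger is a visual judgement made once the data are in hand. The other route offered, transformation, is largely used already.

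**Working it through.** **Inputs from the SAP.** Section 6: n=12 evaluable per group; within-subject SD σw = 0.139 (log scale); planned effect +40%, log difference 0.336; earlier observed effect +22%, ln(17092.6/14022.2) = 0.198, against a different comparator that contained entacapone; test level set by "using a crossover ANOVA with a 0.1 two-sided significance level".

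**Assumption.** Between-subject SD σb is not in the documents. I used 0.20, 0.25, 0.30 and 0.35 on the log scale.

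**The plan's own figure.** SAP 6 states 80% power at 0.336. The standard error of a within-subject difference is σw·√(2/n) = 0.139 × √(2/12) = 0.0567, and 0.336/0.0567 = 5.92. The noncentral t gives 99.995% power (11 df) or 99.998% (30 df), so the 80% does not reproduce. The stated inputs give 80% power at a log difference of 0.144–0.151, a ratio of about 1.15–1.16. I therefore added an effect of 0.145 (ratio 1.16) to the two effects above. The excess power at 40% matters for reading the results.

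**Mechanism.** A paired comparison has variance 2σw²/n. An independent-groups test measures the difference against noise of 2(σw² + σb²)/n. The ratio is 1 + σb²/σw²:

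- σb = 0.20: 1 + 0.0400/0.01932 = 3.07, so the yardstick is √3.07 = 1.75 times too long.
- σb = 0.35: 1 + 0.1225/0.01932 = 7.34, so it is √7.34 = 2.71 times too long.

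**Simulation.** 20,000 trials per cell, n=12, normal data on the log scale, four treatments in equal log steps from A to D, no period effect, 10% two-sided. Kruskal-Wallis and Friedman use the chi-squared reference; signed-rank is exact. The four Kruskal-Wallis values in each cell are for σb = 0.20 / 0.25 / 0.30 / 0.35.

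| True A–D effect | Kruskal-Wallis, A vs D | Signed-rank, A vs D | Kruskal-Wallis, four arms | Friedman |
|---|---|---|---|---|
| None | 1.1 / 0.5 / 0.2 / 0.1% | about 9% | 0.3 / 0.1 / 0.0 / 0.0% | about 10% |
| 16% (0.145) | 36 / 23 / 14 / 9% | about 74% | 11 / 5 / 2 / 1% | about 57% |
| 22% (0.198) | 66 / 50 / 36 / 25% | about 93% | 32 / 17 / 8 / 4% | about 82–83% |
| 40% (0.336) | 99 / 97 / 92 / 84% | about 100% | 92 / 79 / 59 / 41% | 99.8% |

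An exact rank-sum test for A vs D in place of the chi-squared version does slightly worse: 7–32%, 20–62% and 80–99% for the three effects.

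**Where A vs D power falls below one half.** At the 40% effect this needs σb of about 0.50 with n=12, or 0.56 with n=14. At the 22% effect it happens from σb of about 0.26 with n=12, or 0.30 with n=14.

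**The case against.** The strongest reply is that nothing is committed. The test is only an example, transformation is offered beside it, both are only to be considered, and the trigger is a failed residual check on data that are already logged. The primary analysis is fixed in SAS code as a mixed model with a random subject effect, so the pairing is kept where it counts. The error is also in the safe direction: it cannot produce false positives. Conclusions rest partly on the concentration-time profiles, not on p-values alone. All of this stands, and it limits the point to a contingency.

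Two stronger readings are tempting, and the documents do not support them.

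- **That the fallback loses most of its power.** At the plan's own 40% effect, A vs D keeps 84–99% over the assumed range, because the design has power to spare there. Heavy loss appears at smaller effects, in the four-arm test, or with larger between-subject SD, and that SD is not given.
- **That the fallback is likely to be used, for instance on tmax.** One general sentence in SAP 7.2.11 points that way. SAP Table 2, Protocol Table 4 and the output list all treat tmax and t½ as descriptive.

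What the reply does not remove is that the single test named suits none of the within-group comparisons. Kruskal-Wallis would fit only the optional parallel-group comparisons mentioned in SAP 5, and 7.2.8 is not limited to those.

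**Conclusion.** The point holds as a defect in a contingency analysis, not in the planned primary analysis. With n=12, within-subject SD 0.139 and an assumed between-subject SD of 0.20–0.35, Kruskal-Wallis has an actual type I error of about 0–1% where 10% is intended. The cost for A vs D is modest at a 40% effect, and large at effects of 16–22%. At 22% the four-arm test has about 4–32% power where Friedman has about 82–83%.

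That Kruskal-Wallis is the wrong kind of test here follows from the design alone. The size of the loss depends on the assumed between-subject SD and effect, and for the four-arm test also on the equal spacing of treatments. The 16% and 22% effects are illustrations, not the plan's assumption for A vs D. They are relevant mainly because the secondary contrasts isolate one component or one dose step, where smaller effects are plausible.

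**What to change.** In SAP 7.2.8, replace Kruskal-Wallis for within-group comparisons with a within-subject rank method:

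- Pairwise contrasts, including A vs D: Wilcoxon signed-rank on within-subject log differences, with the Hodges-Lehmann estimate and its 90% CI back-transformed to a ratio. This also meets the interval commitment in SAP 7.2.1.
- Four-treatment comparison: Friedman, or Skillings-Mack if some periods are missing.
- Alternatively, a crossover rank analysis that also adjusts for period. Plain signed-rank and Friedman do not, which is a small drawback against the planned model.

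Kruskal-Wallis can stay for the optional parallel-group comparisons if the text says so.

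Separately, make SAP 7.2.11 agree with Table 2 and the output list on whether tmax and t½ are tested or only described. If they are tested, name the paired method and add the tables.

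The cost is about one sentence in 7.2.8, one correction for 7.2.11 and a little programming. No extra data are needed.

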#### **7.2.9 Transformations**

PK parameters (at least AUC and Cmax) will be analysed after logarithm transformation.

#### **7.2.10 Handling of outliers and sensitivity analyses**

If outliers are detected based on residual examination, a sensitivity analysis without the outliers may be performed to evaluate potential impact to the results.

#### **7.2.11 Methods for handling multiple time points**

PK parameters Cmax, AUC, tmax and t1/2 will be calculated and used in statistical comparisons. When modelling PK parameters that are calculated by dosing intervals, treatment by dosing interval interaction will be included in the statistical models.

#### **7.2.12 Descriptive statistics**

The following statistics will be provided for continuous variables: N, mean, SD, min, median and max. In PK variables also geometric mean and coefficient of variation (CV%) will be calculated. Because log-normal distribution, the formula  $CV\% = 100 \times \sqrt{\exp(\sigma^2) - 1}$ , where  $\sigma^2$  is MSE of the statistical analysis of log transformed data, will be used. For categorical variables frequency counts and percentages will be presented. All mean, median, standard deviation, and if feasible quartile values will be presented to one more decimal place than the raw values. Minimum and maximum will be presented to the same precision as the raw values.

All percentages will be rounded to one decimal place, with the exception of 0 and 100, which will be presented as integers.

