### 8.4 Analysis of pharmacokinetic variables

Table 2 lists the PK parameters which will be derived from the concentration-time data of levodopa, carbidopa, 3-OMD and, ODM-104.

Table 2. PK parameters to be calculated for levodopa, carbidopa, 3-OMD and ODM-104.

| Parameter     | Levodopa       | Carbidopa      | 3-OMD          | ODM-104        |
|---------------|----------------|----------------|----------------|----------------|
| $C_{max}$     | X  | X  | X  | X  |
| $C_{max,tau}$ | X  |                |                | X              |

|  |                |                |                |                |
|--|----------------|----------------|----------------|----------------|
| $t_{\max}$                             | X              | X              | X              | X              |
| $t_{\max,\tau}$                        | X              |                |                | X              |
| $C_{\min,\tau}$                        | X  |                |                | X              |
| $C_{\min,\tau,\text{actual}}$          | X  |                |                |                |
| $AUC_{\tau}$                           | X  |                |                | X              |
| $AUC_{0-16}$                           | X  |                |                |                |
| $AUC_{0-24}$                           | X  | X  | X  | X  |
| $AUC_{\infty}$                         | X              |                |                | X              |
| $t_{1/2}$                              | X              |                |                | X              |
| $\lambda_z$                            | X              |                |                | X              |
| $C_{\max}/C_{\min,\tau}$               | X  |                |                |                |
| $C_{\max}/C_{\min,\tau,\text{actual}}$ | X  |                |                |                |
| $C_{\max}/C(16h)$                      | X  |                |                |                |
| $PTF_{\tau}$                           | X  |                |                |                |
| $PTF_{0-16h}$                          | X  |                |                |                |

 Statistical analysis will be performed

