#### 8.4.2 Secondary PK parameters

The secondary PK variable is  $C_{\min,\tau}$ , which is used to describe minimum concentration during the dosing intervals. Statistical evaluation for secondary PK variable will be done using similar methods as for primary variable, except the statistical model will include also the dosing interval as fixed effect.

The following SAS-code for the analysis will be applied:

```
proc mixed data=pkparam2 alpha=0.10;
  class subject trtpcd interval visit;
  model log_auc = trtpcd interval trtpcd*interval visit /
ddfm=KR outp=Resid solution;
random subject*visit;
lsmeans trtpcd trtpcd*interval / diff cl alpha=0.10
adjust=tukey ADJDFE=ROW;
ods output tests3=testCross lsmeans=lsmeansCross
diffs=diffscross;
by group;
run;
```

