##### 14.2 Pharmacokinetic data

|                  |   |
|------------------|---|
| Table 14.2.1.1   | Levodopa concentration (ng/ml)  |
| Table 14.2.1.2.1 | AUC tau (h*ng/mL) of levodopa  |
| Table 14.2.1.2.2 | Statistical analysis for AUC tau of levodopa                           |
| Table 14.2.1.3.1 | AUC 0-24 (h*ng/mL) of levodopa   |
| Table 14.2.1.3.2 | Statistical analysis for AUC 0-24 of levodopa                          |
| Table 14.2.1.4.1 | AUC 0-16 (h*ng/mL) of levodopa   |
| Table 14.2.1.4.2 | Statistical analysis for AUC 0-16 of levodopa                          |
| Table 14.2.1.5   | AUC inf (h*ng/mL) of levodopa  |
| Table 14.2.1.6.1 | C max,tau (ng/mL) of levodopa  |
| Table 14.2.1.6.2 | Statistical analysis for C max,tau of levodopa                         |
| Table 14.2.1.7.1 | C max (ng/ml) of levodopa  |
| Table 14.2.1.7.2 | Statistical analysis for C max of levodopa                             |
| Table 14.2.1.8.1 | C min,tau (ng/mL) of levodopa  |
| Table 14.2.1.8.2 | Statistical analysis for C min,tau (ng/mL) of levodopa                 |
| Table 14.2.1.8.3 | Actual C min,tau (ng/mL) of levodopa                                   |
| Table 14.2.1.8.4 | Statistical analysis for actual C min,tau (ng/mL) of levodopa          |
| Table 14.2.1.9.1 | C max / C min ratio tau of levodopa                         |
| Table 14.2.1.9.2 | Statistical analysis of C max / C min ratio tau of levodopa |

|                   |  |
|-------------------|--|
| Table 14.2.1.9.3  | Actual Cmax / Cmin ratio tau of levodopa                         |
| Table 14.2.1.9.4  | Statistical analysis of actual Cmax / Cmin ratio tau of levodopa |
| Table 14.2.1.10.1 | Cmax / C(16h) of levodopa  |
| Table 14.2.1.10.2 | Statistical analysis of Cmax / C(16h) of levodopa                |
| Table 14.2.1.11   | tmax,tau (h) of levodopa   |
| Table 14.2.1.12   | tmax (h) of levodopa   |
| Table 14.2.1.13   | t1/2 (h) of levodopa   |
| Table 14.2.1.14   | Lambda z of levodopa   |
| Table 14.2.1.15.1 | PTFtau of levodopa   |
| Table 14.2.1.15.2 | Statistical analysis for PTFtau of levodopa                      |
| Table 14.2.1.16.1 | PTF0-16 of levodopa  |
| Table 14.2.1.16.2 | Statistical analysis for PTF0-16 of levodopa                     |

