|              | Median | XXXX.XX      | XXXX.XX      | XXXX.XX      | XXXX.XX      |
|              | Max    | XXXX.X       | XXXX.X       | XXXX.X       | XXXX.X       |

Program: T\_14\_2\_1\_2\_1\_Levodopa AUC\_tau.sas

Date: 23MAY17:08:38

STUDY 3112005

DRAFT

Page: 1 (4)

Table 14.2.1.3.1 AUC0-24 (h\*ng/mL) of levodopa  
Per protocol population

|          |        | A1
(N=XX) | B1
(N=XX) | C1
(N=XX) | D1
(N=XX) |
|----------|--------|--------------|--------------|--------------|--------------|
| AUC0 24h | N      | XX           | XX           | XX           | XX           |
|          | Gmean  | XXXXX.XX     | XXXXX.XX     | XXXXX.XX     | XXXXX.XX     |
|          | Mean   | XXXXX.XX     | XXXXX.XX     | XXXXX.XX     | XXXXX.XX     |
|          | SD     | XXXX.XX      | XXXX.XX      | XXXX.XX      | XXXX.XX      |
|          | CV%    | XX.XX        | XX.XX        | XX.XX        | XX.XX        |
|          | Min    | XXXX.X       | XXXX.X       | XXXX.X       | XXXX.X       |
|          | Median | XXXXX.XX     | XXXXX.XX     | XXXXX.XX     | XXXXX.XX     |
|          | Max    | XXXXX.X      | XXXXX.X      | XXXXX.X      | XXXXX.X      |

Program: T\_14\_2\_1\_3\_1\_Levodopa AUC0-24.sas

Date: 23MAY17:08:40

STUDY 3112005

DRAFT

Page: 1 (8)

Table 14.2.1.3.2 Statistical analysis for AUC0-24 of levodopa  
Per protocol population

Analysis of variance

| Effect                            | Estimate
(Geometric Mean) | Stderr | 90%
Confidence Interval | P-value |
|-----------------------------------|------------------------------|--------|----------------------------|---------|
| Fixed Effects                     |                              |        |                            |         |
| Formulation                       | .                            | .      |                            | X.XXXX  |
| Period                            | .                            | .      |                            | X.XXXX  |
| Least Square Means                |                              |        |                            |         |
| Formulation A1                    | XXXXX.XXX                    | X.XXXX | (XXXXX.XX , XXXXX.XX)      | <.XXXX  |
| Formulation B1                    | XXXXX.XXX                    | X.XXXX | (XXXXX.XX , XXXXX.XX)      | <.XXXX  |
| Formulation C1                    | XXXXX.XXX                    | X.XXXX | (XXXXX.XX , XXXXX.XX)      | <.XXXX  |

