| Formulation D1                    | XXXXX.XXX                    | X.XXXX | (XXXXX.XX , XXXXX.XX)      | <.XXXX  |
| Differences in Least Square Means |                              |        |                            |         |
| Formulation A1 B1                 | X.XXXXXXX                    | X.XXXX | ( X.XXXX , X.XXXX)         | X.XXXX  |
| Formulation A1 C1                 | X.XXXXXXX                    | X.XXXX | ( X.XXXX , X.XXXX)         | X.XXXX  |
| Formulation A1 D1                 | X.XXXXXXX                    | X.XXXX | ( X.XXXX , X.XXXX)         | X.XXXX  |
| Formulation B1 C1                 | X.XXXXXXX                    | X.XXXX | ( X.XXXX , X.XXXX)         | X.XXXX  |
| Formulation B1 D1                 | X.XXXXXXX                    | X.XXXX | ( X.XXXX , X.XXXX)         | X.XXXX  |
| Formulation C1 D1                 | X.XXXXXXX                    | X.XXXX | ( X.XXXX , X.XXXX)         | X.XXXX  |

Program: T\_14\_2\_1\_3\_2\_Levodopa statistical analysis for AUC0-24.sas

Date: 23MAY17:08:40

STUDY 3112005

DRAFT

Page: 1 (5)

Table 14.3.1.1 Summary of adverse events during study treatment (subject and event count)  
Safety population

|               |  | A1
(N=XX)
n (%) | B1
(N=XX)
n (%) | C1
(N=XX)
n (%) | D1
(N=XX)
n (%) |
|---------------|--|-----------------------|-----------------------|-----------------------|-----------------------|
| Subject count | AEs  | X (XX.X)              | X (XX.X)              | X (XX.X)              | X (XX.X)              |
|               | Related AEs                                | X (XX.X)              | X (XX.X)              | X (XX.X)              | X (XX.X)              |
|               | AEs leading to
discontinuation of study |                       |                       |                       |                       |
|               | Mild AEs                                   | X (XX.X)              | X (XX.X)              | X (XX.X)              | X (XX.X)              |
|               | Moderate AEs                               | X (XX.X)              | X (XX.X)              | X (XX.X)              | X (XX.X)              |
|               | Severe AEs                                 |                       |                       |                       |                       |
|               | SAEs                                       |                       |                       |                       |                       |

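### The SAP's only CV% rule puts the model's residual variance into the by-treatment descriptive tables, so every treatment column of a group would show the same CV%, and parameters without a model would have none.

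*SAP*

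**What the plan says.** SAP 7.2.12, on descriptive statistics, states: "In PK variables also geometric mean and coefficient of variation (CV%) will be calculated". It then gives a single log-normal formula for CV%, in which σ² "is MSE of the statistical analysis of log transformed data, will be used". Neither document gives another CV% formula.

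For AUC0-24, SAP 8.4.1 says: "The statistical model will include treatment and period as fixed effects and subject as a random effect". The SAS code there runs by group and has no option for treatment-specific residual variances. For the secondary variable Cmin,tau, the code in SAP 8.4.2 adds dosing interval and its interaction with treatment, and its only random term is "random subject*visit".

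In SAP 10.3, the descriptive template headed "Table 14.2.1.3.1 AUC0-24" has a CV% cell in each treatment column, next to that column's N, geometric mean, mean and SD. The AUCtau template has one such cell for each treatment and interval. The statistical-analysis template 14.2.1.3.2 ends with the block "Differences in Least Square Means" and has no CV% row.

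In SAP Table 2, footnote 1 ("Statistical analysis will be performed") marks only some parameters. Levodopa AUCinf and lambda_z are unmarked, as are ODM-104 AUCtau, Cmax,tau and Cmin,tau. The list of tables in SAP 10.1 gives these a descriptive table only (for example "Lambda z of levodopa"), while protocol 8.4.3 asks for descriptive summaries of all PK variables.

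**The concern.** A model residual variance belongs to a fitted model, not to a treatment column. The rule in 7.2.12 puts it where a reader expects the spread of values on one treatment. Three consequences follow.

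- Within a group, the CV% row cannot differ between treatments, whatever the data show.
- For AUC0-24 the printed figure is a within-subject CV with no label saying so. The SD beside it includes between-subject spread, so the two would describe different things.
- Where no log-scale analysis is planned, the formula has no input.

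The study's PK data are meant to guide the choice of combination for later trials, and AUC0-24 and Cmin,tau are among the variables SAP 8.4.3 names as of main interest. A residual CV read as the by-treatment CV would usually make exposure look more consistent between subjects than it is.

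**Working it through.** **Inputs.** The CV% formula comes from SAP 7.2.12, the model from SAP 8.4.1, and the planning sqrt(MSE) for log AUC0-24, 0.1386, from SAP 6. The documents state no CV% figure, so there is none to reproduce. They also give no between-subject variance; the values used below are assumptions.

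**1. How many distinct CV% values the rule yields.** The fit is by group with one residual variance, so there is one MSE, and one CV%, per group and parameter. A, B, C and D share it. If the per-interval parameters follow the 8.4.2 form, one residual serves 4 treatments × 4 intervals = 16 cells.

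**2. The printed value for AUC0-24.** MSE = 0.1386² = 0.01921. CV% = 100 × sqrt(exp(0.01921) − 1) = 13.93% in every column.

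**3. What a by-treatment CV would be.** With equal within-subject variances, the variance of the log values on one treatment is the MSE plus the between-subject variance, ln(1 + CVb²), where CVb is the between-subject CV. So CV% = 100 × sqrt(exp(0.01921 + ln(1 + CVb²)) − 1).

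| Assumed CVb | Printed CV% | By-treatment CV% |
|---|---|---|
| 0% | 13.9 | 13.9 |
| 10% | 13.9 | 17.2 |
| 30% | 13.9 | 33.3 |
| 50% | 13.9 | 52.4 |

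**4. Direction when within-subject variances differ.** Treatment t is understated if its between-subject plus within-subject variance exceeds the MSE. Under the single subject effect of 8.4.1 this always holds once the between-subject variance exceeds 0.01921, that is, CVb above 13.93%. Below that it can fail. At CVb = 10% the between-subject variance is ln(1.01) = 0.00995, and 0.01921 − 0.00995 = 0.00926, so a treatment with within-subject SD below sqrt(0.00926) = 0.096 would be overstated.

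An example is within-subject SDs of 0.08, 0.10, 0.15 and 0.19. The pooled variance is (0.0064 + 0.0100 + 0.0225 + 0.0361)/4 = 0.01875, so the printed CV is 13.8%. With CVb = 10% the true by-treatment CVs are 12.8, 14.2, 18.2 and 21.7%; the first is overstated and the others understated.

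**5. Sampling behaviour at the planned size.** One group was simulated with 14 subjects, the Group 1 sequences of protocol Table 2, equal within-subject SD of 0.1386, 36 residual degrees of freedom (56 − 1 − 3 − 3 − 13) and 10,000 runs.

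| Assumed CVb | Median MSE-based CV% | Median cell-based CV% | Share of cells where the cell-based value is lower |
|---|---|---|---|
| 0% | 13.8 | 13.6 | 52% |
| 10% | 13.8 | 16.8 | 18% |
| 20% | 13.8 | 23.9 | 1.3% |
| 30% | 13.8 | 32.4 | 0.1% |
| 50% | 13.8 | 50.8 | 0% |

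**6. Per-interval tables.** With subject-by-visit as the only random term, each subject's level in each period is absorbed by that term. The residual is then variation between intervals within a day. It leaves out subject-by-period variance, so it is not an intra-subject CV either. No figure is derived here because the documents give no variance for this model.

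**7. Parameters without a model.** The rule needs an MSE, but Table 2 plans no analysis for the unmarked parameters and SAP 10.1 lists no analysis table for them. Their CV% is therefore undefined.

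**The case against.** The strongest reply is that nothing decisive rests on this CV%. Conclusions come from the concentration profiles and the formal analyses, and the arithmetic CV can be had from the Mean and SD in the same column. Four identical values would also be noticed. That stands, and it limits the point to descriptive reporting.

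Second, cell-specific values may have been intended. The templates reserve a CV% cell for each treatment and interval, and the 8.4.1 code saves no covariance-parameter output. That is possible, but 7.2.12 names the MSE of the statistical analysis, and SAP 6 uses sqrt(MSE) in its ordinary sense of within-subject variability. A programmer who follows the text prints one repeated number; one who computes by column departs from it. The wording needs correcting either way.

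Third, SAP 7.2.11 says AUC, Cmax, tmax and t1/2 enter statistical comparisons, which could be read to cover AUCinf. This conflicts with Table 2 and the table list. It weakens AUCinf as an example and is why tmax and t1/2 are not used here. It names neither lambda_z nor ODM-104 Cmin,tau. The log-scale variance of lambda_z equals that of t1/2, but the SAP does not say to borrow it. The example templates show only modelled parameters, so this part rests on the wording of 7.2.12 and the table list.

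Fourth, the size depends on an assumed between-subject variance, and the planning MSE comes from an earlier study with a different comparator. Both are true. The identity of the columns does not depend on either.

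Fifth, the 16-cell statement applies the Cmin,tau code to AUCtau. SAP 7.2.11 requires only the interaction there, so this is an inference, though any single-residual model gives the same result.

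**Conclusion.** The concern holds: 7.2.12 as written yields the wrong dispersion statistic for the by-treatment tables. For AUC0-24 each group would show one pooled within-subject CV%, 13.9% at the planning value. If within-subject variances are similar, this will typically understate the by-treatment CV: not at all with no between-subject variance, and 13.9% against 33.3% at an assumed between-subject CV of 30%. With the MSE at its planning value, understatement is certain for every treatment once the between-subject CV passes 13.9%; below that, the direction can reverse for a treatment with low within-subject variance. For parameters with no planned analysis, the CV% is undefined. Inference is untouched, and SD and range by treatment remain available. The change is worth making before the tables are programmed, but it does not threaten the trial's conclusions.

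**What to change.** In SAP 7.2.12, define the by-treatment (and, where relevant, by-interval) geometric CV% as 100 × sqrt(exp(s²) − 1), with s² the sample variance of the log values in that cell. This also covers positive-valued parameters that have no model. Keep the MSE-based figure, but report it once per model and group in the statistical-analysis tables through a new row in templates such as 14.2.1.3.2. Label it as the model residual CV%; for AUC0-24 it may be called the intra-subject CV%. The cost is one or two SAP sentences, one template row and a small programming change.
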